4. STUDY POPULATION

4.1. Type and Number of Subjects

Approximately 500 adult subjects with plaque psoriasis will be enrolled in the study at approximately 50 to 60 study sites in the US and Canada.

Protocol violations from inclusion and exclusion criteria are prohibited because ineligible study subjects can potentially jeopardize the scientific integrity of the study, regulatory acceptability, or subject safety. Therefore, adherence to the criteria as specified in the protocol is essential.

4.2. Inclusion Criteria

Each subject must meet all of the following criteria to be eligible to participate in the study:

1. Male and female subjects ages 18 to 75 years with clinical diagnosis of chronic plaque psoriasis and stable disease for at least 6 months prior to the study
2. Body surface area involvement $\geq 3\%$ and $\leq 20\%$ (the subject's scalp, palms, fingernails, toenails, and soles should be excluded from the %BSA calculations).
3. A PGA score of 2 (mild), 3 (moderate) or 4 (severe) at screening and baseline (pre-randomization). Subjects with mild and severe psoriasis will be limited to approximately 10% each of the total randomized population; the majority of the enrolled subjects (approximately 80%) will have a PGA of 3, signifying moderate disease.
4. Females of child-bearing potential and male subjects who are engaging in sexual activity that could lead to pregnancy must use at least 1 of the following adequate birth control methods while on study and for 4 weeks after the last exposure to study drug. Acceptable contraception methods are:
 - Male partner with vasectomy, OR
 - Male condom AND partner use of one of the contraceptive options below:
 - Spermicide
 - Contraceptive subdermal implant that meets effectiveness criteria including a $< 1\%$ rate of failure per year, as stated in the product label
 - Intrauterine device or intrauterine system that meets effectiveness criteria including a $< 1\%$ rate of failure per year, as stated in the product label
 - Oral contraceptive, either combined or progestogen alone
 - Injectable progestogen
 - Contraceptive vaginal ring
 - Percutaneous contraceptive patches

NOTE: Subjects using hormonal contraceptives must have been on a stable dose for at least 4 weeks before baseline.

These allowed methods of contraception are only effective when used consistently, correctly and in accordance with the product label. The Investigator is responsible for ensuring that subjects understand how to properly use these methods of contraception.

Non-child-bearing potential is defined as premenarchal or pre-menopausal females with a documented bilateral tubal ligation, bilateral oophorectomy (removal of the ovaries) or

hysterectomy, or hysteroscopic sterilization; or postmenopausal females defined as a cessation of menses for at least 12 months without an alternative medical cause. In questionable cases a blood sample with simultaneous follicle stimulating hormone (FSH) > 40 IU/mL is confirmatory. Documented verbal history from the subject is acceptable.

Subjects who are abstinent are eligible, but they must agree to use one of the birth control methods listed above if they start engaging in sexual activity that could lead to pregnancy during the study.

Female subjects of childbearing potential must have a negative serum pregnancy test at Screening and negative urine pregnancy test at Baseline (Day 1).

5. Capable of giving written informed consent, as applicable, which includes compliance with the requirements and restrictions listed in the informed consent form (ICF); written informed consent must be obtained prior to any study related procedures.

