6.3.4. Clinical Safety Laboratory Assessments

All protocol-required laboratory assessments must be conducted in accordance with the Study Reference Manual or Laboratory Manual and the protocol Schedule of Assessments ([Table 1](#)). Laboratory requisition forms must be completed, and samples must be clearly labeled with the subject number, protocol number, site/center number, and visit date. Details for the preparation and shipment of samples will be provided by the laboratory and are detailed in the Study Reference Manual or the Laboratory Manual. Reference ranges for all safety parameters will be provided to the site by the laboratory responsible for the assessments.

A list of clinical laboratory tests and parameters is provided in [Table 3](#).

All laboratory tests with values that are considered clinically significantly abnormal during participation in the study should be repeated until the values return to normal or baseline. If such values do not return to normal within a period judged reasonable by the Investigator, the etiology should be identified, if possible, and the Sponsor notified.

Table 3: Laboratory Tests

Diagnostic Screening Tests		

 • HBsAg • Hepatitis C antibody • Anti-HBc 	
 • Pregnancy tests: (serum at Screening and urine at other visits; women of CBP only) • FSH (as needed in women of non-CBP only) • At the Investigator’s discretion, subjects may be screened for alcohol and illicit drug use. 	
Serum Chemistry		

 • BUN • Creatinine • Glucose (fasting not required) • Sodium • Potassium • Chloride 	
 • Total carbon dioxide • Calcium • AST • ALT • Alkaline phosphatase 	
 • Uric acid • Total bilirubin (+fractionated if required) • Total protein • Albumin
Hematology		

 • Platelet count • RBC count • WBC count (absolute) • Reticulocyte count • Hemoglobin • Hematocrit 	
 • RBC Indices: • MCV • MCH • MCHC • Reticulocyte percentage 	
 • WBC Differential: • Neutrophils • Lymphocytes • Monocytes • Eosinophils • Basophils
Urinalysis		

 • Specific gravity • Microscopic examination (if blood or protein is abnormal) 	
 • Dipstick: pH, Glucose, Protein, Blood Ketones 	

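### The FSH level called confirmatory of postmenopausal status is printed as > 40 IU/mL (40,000 mIU/mL), so read literally the FSH test cannot confirm it; other routes remain and the error is conservative

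*Protocol*

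**What the plan says.** Inclusion criterion 4 in Protocol Section 4.2 sets the contraception requirement and then defines who is not of child-bearing potential. There are two main routes. The first is surgical: a documented tubal ligation, oophorectomy, hysterectomy or hysteroscopic sterilization. The second is menopause: "postmenopausal females defined as a cessation of menses for at least 12 months without an alternative medical cause".

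FSH comes in only as a back-up: "In questionable cases a blood sample with simultaneous follicle stimulating hormone (FSH) > 40 IU/mL is confirmatory". The sentence after it adds: "Documented verbal history from the subject is acceptable". The Synopsis repeats the criterion with the same number and unit.

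Table 3 in Section 6.3.4 names the test among the diagnostic screening tests, as "FSH (as needed in women of non-CBP only"), without a unit, cut-off or range. The text above that table says: "Reference ranges for all safety parameters will be provided to the site by the laboratory responsible for the assessments". SAP Section 12.9.3 likewise has a central laboratory supply the normal ranges and range indicators for the safety laboratory data. Neither place mentions an FSH threshold. The summary of changes in Appendix 9 lists no change to the FSH sentence.

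**The concern.** A confirmatory cut-off is useful only if some samples can exceed it. The printed unit is IU per millilitre. Converted to a per-litre or milli-unit scale, the cut-off becomes 40,000, far above any serum FSH that could reasonably be expected. The number and the unit therefore do not appear to belong together.

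The sentence is eligibility text, not background. Section 4.1 requires the criteria to be followed as written, and Section 6 rules out waivers except for immediate safety concerns. The classification also has consequences. It decides whether a woman must use contraception and have the serum and urine pregnancy tests in Table 1, which are among the measures Section 1.3.1.3 sets against the embryo-fetal findings in animals. If the cut-off cannot be reached, the only laboratory test named for settling a doubtful menopausal status does nothing when applied as written.

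**Working it through.** **Inputs**
- Printed cut-off: > 40 IU/mL (Protocol Section 4.2, criterion 4, and Synopsis).
- FSH range: none in either document. Assumption: the highest FSH found in human serum lies somewhere between 100 and 500 mIU/mL. The range is deliberately wide.

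**Step 1. Is there a plan figure to reproduce?** No. The cut-off is stated, not derived from other inputs, so only its unit can be checked.

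**Step 2. Convert the unit.**
- 1 IU = 1,000 mIU, so 40 IU/mL = 40 × 1,000 = 40,000 mIU/mL.
- 1 L = 1,000 mL, so 40 IU/mL = 40 × 1,000 = 40,000 IU/L.

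The two results agree because 1 mIU/mL and 1 IU/L are the same concentration. The printed cut-off is thus 1,000 times what the number 40 would mean on either of those scales. This factor is exact and needs no assumption.

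**Step 3. Compare with the assumed maximum.** Ratio = 40,000 ÷ assumed maximum in mIU/mL.

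| Assumed maximum serum FSH | Same value in IU/mL | Cut-off ÷ maximum |
|---|---|---|
| 100 mIU/mL | 0.1 | 400 |
| 200 mIU/mL | 0.2 | 200 |
| 500 mIU/mL | 0.5 | 80 |

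Nowhere in this range can a sample exceed the cut-off. Even the upper end would have to be too low by a factor of 80 before one could.

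**Step 4. Trace what fails and what does not, on a literal reading.**
- Postmenopausal status by at least 12 months without menses: does not use FSH, unaffected.
- Surgical routes: do not use FSH, unaffected.
- Documented verbal history: accepted in the sentence after the cut-off, unaffected.
- Confirmation by FSH in a questionable case: cannot occur.

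**Step 5. Direction of the error.** A woman whose status remains in question is not moved out of the child-bearing group. She keeps the contraception duty and the pregnancy tests. Under criterion 4 she can still enrol if she uses a listed method or is abstinent, and if her serum and urine tests are negative. An unreachable cut-off cannot cause a fertile woman to be classed as infertile.

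**Step 6. Effect on the statistics.** The cut-off does not enter the sample size, the analysis populations, the endpoints or any test in Section 10 of the protocol or in the SAP.

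**The case against.** The strongest reply is that this is a unit slip with little practical effect. It touches only questionable cases, whose number the documents do not give. FSH is not the deciding criterion, and the literal error leans towards more contraception and more testing. The two places that state the cut-off agree with each other, so there is no internal contradiction, and the problem becomes visible only with an FSH range from outside the documents. All of this stands, and it keeps the point modest. It does not make the text right: the conversion is exact, and the conclusion survives a very wide assumed range. The same unit in two places also makes a one-off error in reading the PDF unlikely.

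A reader might draw three stronger conclusions, which the documents do not support.

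- *No questionable case can ever be confirmed as of non-child-bearing potential.* Only confirmation by FSH fails. Verbal history is accepted immediately after the cut-off. Whether it is meant to settle a questionable case is open on the text, so a figure of zero confirmations does not follow.
- *Women are wrongly excluded, or exposed to embryo-fetal risk.* Step 5 shows neither. The cost of the literal reading is some unnecessary contraception and testing.
- *Every site must substitute its own unit, so practice will differ between sites.* Nothing in the documents shows this. The SAP refers to a central laboratory, and the protocol has the responsible laboratory supply its ranges. Neither statement names FSH, so they do not settle the matter, but they make site-by-site substitution less likely.

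It is also tempting to assume that 40 is right and only the unit is wrong. The documents do not establish that either.

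**Conclusion.** The point holds in a limited form. An eligibility threshold is printed with a number and unit that together give 40,000 mIU/mL, which is 80 to 400 times an assumed maximum serum FSH of 100 to 500 mIU/mL. Read literally, the FSH test cannot confirm postmenopausal status. The 1,000-fold conversion is exact. That the level cannot be reached rests on the assumed range, with a margin of at least 80-fold.

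The effect is confined to questionable cases not resolved by 12 months without menses, a surgical route or documented verbal history, and it is conservative for those women. It has no bearing on power, efficacy or any planned analysis. It still deserves correction, because sites are told to apply the criteria as written and the correction costs almost nothing.

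**What to change.** The sponsor should check both the number and the unit of the FSH cut-off against the unit in which the laboratory reports FSH. The sentence in Section 4.2, criterion 4, and its copy in the Synopsis should then be corrected so that number and unit agree with each other and across the two places. Showing the unit beside FSH in Table 3 is optional. This review proposes no replacement threshold and no change to the clinical rule.

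The cost is a text correction in two places, which can go into the next protocol amendment. It adds no test or visit and requires no change to the SAP.

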4.3. Exclusion Criteria

A subject who meets any of the following criteria will be excluded and considered ineligible for participation in the study:

1. Psoriasis other than plaque variant
2. Any sign of infection of any of the psoriatic lesions
3. Concurrent conditions or history of other diseases:
 - a. Immunocompromised (eg, lymphoma, acquired immunodeficiency syndrome) or medical history of positive human immunodeficiency virus (HIV) antibody at Screening
 - b. Chronic or acute systemic infection requiring treatment with systemic antibiotics, antivirals, antiparasitics, antiprotozoals, or antifungals within 4 weeks prior to the Baseline visit
 - c. Acute active bacterial, fungal, or viral (herpes simplex, herpes zoster, chicken pox) skin infection within 1 week prior to the Baseline visit
 - d. Significant dermatologic or inflammatory condition other than plaque psoriasis that, in the Investigator's opinion, would make it difficult to interpret data or assessments during the study
4. Screening alanine aminotransferase (ALT) or aspartate aminotransferase (AST) $\geq 1.5x$ the upper limit of normal (ULN)
5. Screening total bilirubin $> 1.5 x$ ULN; total bilirubin $> ULN$ and $\leq 1.5 x$ ULN is acceptable if bilirubin is fractionated and direct bilirubin $< 35\%$.
6. Corrected QT (QTcF) interval > 475 msec.
7. Current or chronic history of liver disease, known hepatic or biliary abnormalities (with the exception of Gilbert's syndrome or asymptomatic gallstones), presence of hepatitis B surface antigen (HBsAg), or positive hepatitis C antibody test result, or a positive anti-hepatitis B core antigen (anti-HBc) result. Subjects with a history of HCV infection who were medically cured and have an undetectable viral load are eligible to enroll. Subjects with a history of stable non-alcoholic fatty liver disease without evidence of active inflammation (elevated ALT/AST $\geq 1.5x$ ULN) or cirrhosis are eligible to enroll.
8. Ultraviolet (UV) light therapy or prolonged exposure to natural or artificial sources of UV radiation (eg, phototherapy, tanning beds/booths, or therapeutic sunbathing) within

- 4 weeks prior to the Baseline visit and/or plans to have such exposures during the study which could potentially impact the subject's psoriasis (as determined by the Investigator).
9. Use of any prohibited medication within the indicated period before the Baseline visit.
- NOTE: Prohibited concomitant medications, therapy, etc., during the defined period are as listed in the bullets below. If a subject requires any of these medications throughout the study period, he/she may be excluded from or discontinued from the study.
- Minimum of 5 half-lives for biologic agents: eg, 12 months for rituximab; 8 months for ustekinumab; 5 months for secukinumab; 12 weeks for golimumab; 10 weeks for ixekizumab; 8 weeks for infliximab, adalimumab, or alefacept; and 4 weeks for etanercept.
 - 4 weeks for systemic treatments: cyclosporin, interferon, methotrexate, apremilast, tofacitinib, mycophenolate, thioguanine, hydroxyurea, sirolimus, azathioprine, other systemic immunosuppressive or immunomodulating agents, fumaric acid derivatives, vitamin D3 and analogs (> 5000 IU / day), retinoids (eg, acitretin, isotretinoin), psolarens, corticosteroids, or adrenocorticotrophic hormone analogs.
 - 2 weeks for immunizations with a live viral component; drugs known to possibly worsen psoriasis, such as beta-blockers (eg, propranolol), lithium, iodides, angiotensin-converting enzyme inhibitors, and indomethacin, unless on a stable dose for > 12 weeks.
 - With the exception of non-medicated emollients, 2 weeks for topical treatments including corticosteroids, antihistamines, immunomodulators, anthralin (dithranol), Vitamin D derivatives (eg, calcipotriene, calcipotriol), retinoids (Note: 4 weeks for tazarotene), or coal tar.
10. A history of or ongoing serious illness or medical, physical, or psychiatric condition(s) that, in the Investigator's opinion, may interfere with the subject's participation in the study and ability to understand and give informed consent.
11. Pregnant females as determined by positive serum (screening) or urine (baseline) human chorionic gonadotropin test at screening or prior to dosing.
12. Lactating females
13. History of sensitivity to the study drugs, or components thereof or a history of drug or other allergy that, in the opinion of the Investigator or Medical Monitor, contraindicates the subject's participation in the study.
14. The subject has received an investigational product within the following time period prior to the first dosing day in the current study: 30 days, 5 half-lives, or twice the duration of the biological effect of the study drug (whichever is longer).
15. Current or a history of cancer within 5 years except for adequately treated skin basal cell carcinoma, squamous cell carcinoma or carcinoma in situ of the cervix (surgical excision or electrodesiccation and curettage).
16. Subjects with active systemic infection that required oral, intramuscular, or intravenous administration of antibiotics, antifungal or antiviral agents within 4 weeks of Baseline/Day 1.
17. Concurrent skin lesions in the treatment area that, in the opinion of the Investigator, would either interfere with study evaluations or affect the safety of the subject.

18. Subjects with advanced disease or abnormal laboratory test values that could affect the safety of the subject or the implementation of this study.
19. Previous known participation in a clinical study with tapinarof.
20. Evidence of significant hepatic, renal, respiratory, endocrine, hematologic, neurologic, psychiatric, or CV system abnormalities or laboratory abnormality that will affect the health of the subject or interfere with interpretation of the results.

4.4. Lifestyle Restrictions

Subjects must avoid UV light, phototherapy, and excessive sun exposure throughout the study. When prolonged exposure cannot be avoided, use of sunscreen products (except on psoriasis plaques) and protective apparel are recommended.

4.5. Screening/Baseline Failures

To determine subject eligibility at Screening and Baseline, a single repeat of tests or procedures may be allowed at the discretion of the Investigator; the Medical Monitor should be consulted if needed.

Screen failures are defined as subjects who consent to participate in the clinical study but are not subsequently randomized. A minimal set of screen failure information is required to ensure transparent reporting of screen failure subjects to meet the Consolidated Standards of Reporting Trials publishing requirements and to respond to queries from regulatory authorities. Minimal information includes demography, screen failure details, eligibility criteria, and any SAEs.

4.6. Withdrawal Criteria

A subject may voluntarily discontinue treatment and/or withdraw from participation in this study at any time at his/her own request, or may be discontinued from study treatment at any time at the discretion of the Investigator for safety, behavioral, compliance, or administrative reasons. Subjects withdrawn from the study will not be replaced.

4.6.1. Reasons for Withdrawal from the Study

Study drug will be discontinued for any of the following reasons:

- Subject has an AE that is considered to be related to study drug or procedures AND is severe enough to warrant treatment discontinuation, as determined by the Investigator (Section 8.1).
- Subject requires concurrent prohibited medication during the study. If, in the opinion of the Investigator and the study Medical Monitor, such medication will not interfere with the conduct or interpretation of the study or compromise the safety of the subject, then the subject may continue to receive study drug. If the subject is discontinued from study drug, they may remain in the study for safety assessments as needed, at the discretion of the Investigator and Medical Monitor.
- Pregnancy
- Any Grade 3 or 4 AE considered causally related to study drug (Section 8.2.2)

Study drug may be discontinued for any of the following reasons:

- Subject noncompliance

- Investigator noncompliance
- Discontinuation of the study at the request of the Sponsor, regulatory agency, or an Institutional Review Board (IRB)/Independent Ethics Committee (IEC).

If a subject meets a withdrawal criterion during treatment, an Early Termination visit will be required (Section 7.5).

4.6.2. Withdrawal Procedures

The primary reason for the discontinuation of study drug and/or withdrawal from study must be recorded in the source document and on the electronic case report form (eCRF). If a subject is prematurely discontinued from study drug(s), the Investigator must make every effort to perform an Early Termination Visit (Section 7.5) and document the primary reason for withdrawal.

Should a subject fail to attend a required study visit, the site should attempt to contact the subject and reschedule the missed visit as soon as possible. The site should also counsel the subject on the importance of maintaining the assigned visit schedule and ascertain whether the subject wishes to and/or should continue in the study based on previous noncompliance. In cases where the subject does not return for the rescheduled visit or cannot be reached to reschedule the missed visit, the site should make every effort to regain contact with the subject so that they can appropriately be withdrawn from the study with a primary reason of “Lost to Follow-up”.

4.7. Lost to Follow-Up

A subject is considered lost to follow-up if he/she repeatedly fails to return to the study site for scheduled visits and is unable to be contacted by the study site. The following actions must be taken if a subject fails to return to the clinic for a required study visit:

- The site must attempt to contact the subject and reschedule the missed visit as soon as possible and counsel the subject on the importance of maintaining the assigned visit schedule and ascertain whether or not the subject wishes to and/or should continue in the study.
- Before a subject is deemed lost to follow-up, the Investigator or designee must make every effort to regain contact with the subject (where possible, 3 telephone calls and, if necessary, a certified letter to the subject’s last known mailing address or local equivalent methods). These contact attempts should be documented in the subject’s medical record.
- Should the subject continue to be unreachable, he/she will be considered to have withdrawn from the study with a primary reason of lost to follow-up.

